9.11.8 Reporting of Pregnancy

Not applicable given all enrolled children will not be of childbearing potential.

9.12 UNANTICIPATED PROBLEMS

9.12.1 Definition of Unanticipated Problems (UP)

Any incident, experience, or outcome that meets all of the following criteria:

- Unexpected in terms of nature, severity, or frequency given (a) the research procedures that are described in the protocol-related documents, such as the Institutional Review

Board (IRB)-approved research protocol and informed consent document; and (b) the characteristics of the participant population being studied; and

- Related or possibly related to participation in the research (“possibly related” means there is a reasonable possibility that the incident, experience, or outcome may have been caused by the procedures involved in the research); and
- Suggests that the research places participants or others (which may include research staff, family members or other individuals not directly participating in the research) at a greater risk of harm (including physical, psychological, economic, or social harm) than was previously known or expected.

9.12.2 Reporting Procedures to the FMPOS EC

The USTTB PI is responsible for reporting per FMPOS EC reporting requirements. All UPs, major protocol deviations, all non-compliance, new information that might affect the willingness of a subject to enroll or remain in the study, and any suspension or termination of research activity will be reported to the FMPOS EC within 7 calendar days of investigator awareness. Any death of a research subject that is possibly, probably, or definitely related to the research will be reported within 24 hours of investigator awareness.

The following events will be reported to the FMPOS EC as a high-level summary at the time of continuing review:

- AEs and SAEs that are not UPs, as a narrative summary indicating whether these events were within the expected range.
- Minor and major protocol deviations.
- UPs reported to the FMPOS EC.
- Non-compliance reported to the FMPOS EC that is not related to a protocol deviation.

10. STATISTICAL CONSIDERATIONS

This section describes the statistical analyses of primary and secondary study objectives. Further details, including methods for assessing exploratory objectives, are described in a separate statistical analysis plan to be generated prior to unblinding. Any changes to analyses described in the protocol or statistical analysis plan will be fully disclosed in the clinical study report.

10.1 STATISTICAL HYPOTHESIS

Primary Endpoints

Safety: The primary safety endpoint is the proportion of vaccinees experiencing related SAEs from V1 to 26 weeks after V3. There is no formal hypothesis test associated with this primary safety endpoint. Rather, the proportion of subjects experiencing related SAEs will be presented for each arm separately using frequencies, percentages, and descriptive 95% confidence intervals (CIs).

Efficacy: the primary efficacy endpoint is the vaccine efficacy against *malaria with symptoms*. For this protocol, there is a primary and a secondary case definition of *Pf malaria with symptoms*.

The primary case definition is as follows:

Pf malaria with symptoms is defined as a positive thick blood smear at a density of >1000 P/uL plus:

- Measured axillary temperature ≥ 37.5 degrees Celsius or history of fever (subjective or objective) in the last 24 hours, or,
- Symptoms of malaria –
 - Verbal individual (individual able and willing to answer questions): A verbal individual is considered symptomatic if reporting at the time of evaluation at least two of the following symptoms/symptom groups: headache, chills and/or rigors, malaise and/or fatigue, dizziness and/or light-headedness, myalgias and/or arthralgias; or
 - Non-verbal individual (small child or any individual unable or unwilling to answer questions): A non-verbal individual is considered symptomatic if manifesting at the time of evaluation at least two of the following signs/sign groups: drowsiness, irritability and/or fussiness, inability and/or refusal to eat or drink, prostration; or
- Any individual: Signs of severe malaria (e.g. impairment of consciousness, severe anemia, hemoglobinuria, acute kidney injury, etc.).

The secondary case definition is as follows:

Pf malaria with symptoms is defined as a positive thick blood smear at a density of > 0 P/uL plus:

- Measured axillary temperature ≥ 37.5 degrees Celsius or history of fever (subjective or objective) in the last 24 hours, or,
- Symptoms of malaria as defined in the primary case definition; or
- Meeting criteria for severe malaria

The formal hypothesis associated with the primary efficacy endpoint is a superiority test of

$$H_0: VE = 0 \text{ versus } H_A: VE < > 0$$

(equivalently, $H_0: HR = 1$ vs. $H_A: HR < > 1$). The primary efficacy hypothesis test will be conducted at the two-sided $\alpha=0.05$ significance level, restricted to subjects in the mITT population (defined below in **Section 9.3**).

The primary efficacy endpoint will be assessed over all participants, the vaccinated versus controls.

Secondary Endpoints

Safety: The secondary safety endpoints include the related SAEs as well as all other measures of safety and tolerability – unsolicited AEs, laboratory abnormalities, and solicited AEs.

Efficacy: The secondary efficacy endpoint is the vaccine efficacy against Pf *malaria*.

Pf *malaria* is defined as:

- At least one unambiguous asexual parasite on thick blood smear identified by two independent microscopists after each examining 0.50 μ L of blood in a study participant

10.2 SAMPLE SIZE DETERMINATION

Power calculations for safety analysis:

The goal of the safety evaluation for this study is to identify safety concerns associated with product administration. The ability of the study to detect serious adverse events (SAEs) can be expressed by the true event rate above which at least 1 SAE would likely be observed and the true event rate below which no events would likely be observed. Specifically, within an arm of size $n=120$, there is a 90% chance of observing no event if the true rate is no more than 0.08%, and a 90% chance of observing at least 1 event if the true rate is no more than 1.9%.

Probabilities of observing 0, 1, and 2 or more events within an arm of size 120 are presented in **Table 13**, for a range of possible true adverse event rates. These calculations provide a more complete picture of the sensitivity of this study design to identify potential safety problems with the vaccine.

Table 13. Probability of observing 0, 1 and 2 or more events, within an arm of size 120 for different true event rates.

True event rate (%)	Pr(0/120)	Pr(1/120)	Pr(2+/120)
1	0.299	0.363	0.338
3	0.026	0.096	0.878
5	0.002	0.013	0.984
10	<0.001	<0.001	>0.999

An alternative way of describing the statistical properties of the study design is in terms of the 95% confidence interval for the true rate of an adverse event based on the observed data. **Table 14** shows the 2-sided 95% confidence intervals for the probability of an event based on a particular observed rate. If none of the 120 participants in an arm in the main study experience a safety event, the 95% 2-sided upper confidence bound for the true rate of such events in the total vaccinated population is 0.030.

Table 14. Two-sided 95% confidence intervals based on observing a particular rate of safety endpoint arms for an arm of size 120.

Observed event rate	95% Confidence interval (%)
0/120	(0.000, 0.030)
1/120	(0.000, 0.046)
2/120	(0.002, 0.059)
3/120	(0.005, 0.071)
4/120	(0.009, 0.083)
5/120	(0.014, 0.095)
6/120	(0.019, 0.106)

The sample size determination is mainly based on the assessment of efficacy, which will be shown below.

Power calculations for efficacy analysis:

The primary efficacy endpoint is the efficacy against *Pf malaria with symptoms*. The vaccine efficacy will be assessed by comparing the vaccinated versus the controls.

Based on recent data from Bancoumana, the symptomatic malaria rate under the control is very likely above 0.35 for children of age 6-10. We estimate a sample size of 120 per arm will allow reasonable power to detect the between-arm difference.

Table 15 presents the power calculation for detecting vaccine efficacy based on a two-sided log-rank test with the familywise type I error of 0.05. In the power calculation, vaccine efficacy is 1 minus the probability of *Pf malaria with symptoms* among the vaccinated divided by the probability of *Pf malaria with symptoms* among the controls. A drop-out rate of 10% is assumed.

With 240 subjects in the two arms, this study has over 80% power to detect the vaccine efficacy if the *Pf malaria with symptoms* rate is no less than 0.35 under the control and the vaccine efficacy is no less than 0.5.

In order to allow a booster study to proceed during a second transmission season if VE is 50% or greater in the first year, an additional 10% dropout rate has been assumed and 14 participants added for a total sample size of approximately 134 in each arm in the first year.

Table 15. Power calculation for plausible Pf *malaria with symptom* rates for two-sided log-rank test under type 1 error rate of alpha=0.05.

Pf malaria with symptoms rate under control	Vaccine efficacy	Power(%) (90 per arm)	Power(%) (100 per arm)	Power(%) (110 per arm)	Power(%) (120 per arm)	Power(%) (130 per arm)	Power(%) (140 per arm)
0.3	0.4	43	47	50	54	57	60
	0.5	62	66	70	74	77	80
	0.6	79	83	86	89	91	93
0.35	0.4	50	55	59	62	66	69
	0.5	70	75	79	82	85	88
	0.6	86	89	92	94	95	97
0.4	0.4	58	63	67	71	74	77
	0.5	78	82	86	88	91	93
	0.6	91	94	96	97	98	98
0.5	0.4	73	78	81	85	87	90
	0.5	90	92	95	96	97	98
	0.6	97	98	99	99	100	100
0.6	0.4	86	89	92	94	96	97
	0.5	96	98	99	99	99	100
	0.6	99	100	100	100	100	100

10.3 POPULATIONS FOR ANALYSES

The following analysis populations will be used when describing subject disposition and performing statistical analyses:

- The **Screened Population** includes all subjects who are screened and provide informed consent, regardless of whether the subject is randomized or treated. This population will be used to fully account for subject disposition.

- The **Intention to Treat (ITT) Population** is a subset of the screened population that is deemed eligible to participate in the study, is randomized to a treatment group, receives *at least one injection* with PfSPZ Vaccine or placebo, and contributes evaluable person-time to the risk set.
- The **Modified Intention to Treat (mITT) Population** includes all subjects who are deemed eligible to participate, are randomized, receive *all three injections* of vaccine or placebo, and contribute evaluable person-time to the risk set, including subjects to whom V2 and/or V3 is administered out of the pre-specified time window or an incomplete injection is given, defined as an estimated injection volume of >10% and < 80%.
- The **According to Protocol (ATP) Population** is a subset of the mITT Population, including subjects who complete the vaccination series per protocol and contribute evaluable person-time to the risk set.

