10.4.2 Safety Analyses

The primary safety endpoint is the occurrence of an SAE between V1 and 26 weeks after V3 which is at least possibly related to treatment. Serious AEs which meet this definition will be summarized in frequency tables and listings according to system organ class, preferred term, relatedness, and severity. The primary safety analysis will be performed using the ITT population and according to treatment received at V1, regardless of any randomization or allocation errors. All SAEs will be coded using the Medical Dictionary for Regulatory Activities (MedDRA) and summarized using frequencies, proportions, and exact 95% CIs for proportions. Rates of SAEs (overall and for any system organ class or preferred term with at least 5 events in either group) will be compared using two-sided 0.05 level Fisher's Exact Tests.

Secondary safety endpoints include the occurrence of unsolicited AEs, laboratory abnormalities, and solicited AEs in the ITT population. Unsolicited AEs documented from V1 to 14 days following V3 will be coded using MedDRA and summarized in frequency tables according to system organ class, preferred term, relatedness, and severity. Summaries will be provided overall and according to the vaccination number (1, 2, or 3) immediately prior to AE onset. Rates of unsolicited AEs (overall and for any system organ class or preferred term with at least 5 events in either group) will be compared using two-sided 0.05 level Fisher's Exact Tests. Adverse events leading to premature discontinuation from the study will be listed separately. Clinically relevant laboratory abnormalities recorded in the 14 days after V3 will be summarized in frequency tables by type, grade, and clinical relevance.

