10.4.3 Efficacy Analysis

9.4.3.1 Primary: VE against Pf *malaria with symptoms*

The primary efficacy analysis will be the modified Intention to Treat (mITT).

The primary efficacy analysis will be based on time to the first Pf *malaria with symptoms*. Entry into the risk set begins on the latter of a) 14 days after completing the primary vaccination series (V3 + 14 days) or b) 28 days after initiating treatment for a parasitemia event that was detected on or before V3 + 14 days, whichever comes later. Time-to-event is defined as the number of days between entry into the risk set and date of first Pf *malaria with symptoms*; subjects who do not experience the event by 26 weeks after V3 will be censored from the primary analysis or earlier date of last negative TBS result.

The survival patterns will be described by Kaplan-Meier curves for each arm and compared by the logrank test between two arms. The protective efficacy will be assessed from the Cox proportional hazards model with treatment arm as the regressor, and the vaccine efficacy will be estimated as one minus the hazard ratio.

As a secondary efficacy analysis, the cumulative probability of Pf *malaria with symptoms* through 26 weeks post V3 will be presented for each treatment arm and compared across arms based on Kaplan-Meier estimates along with 95% confidence intervals. This estimation accounts for right censoring and the comparison should be equivalent to Fisher's exact test in case of no censoring.

Sensitivity analyses will include an ITT and ATP analysis with entry into the risk set as with the mITT analysis, and ATP analyses with entries into the risk set at time of first vaccination and at V3.

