3.2 Efficacy Analysis

3.2.1 Primary: VE against Pf malaria with symptoms

The primary efficacy analysis will be the modified Intention to Treat (mITT).

The primary efficacy analysis will be based on time to the first Pf malaria with symptoms. Entry into the risk set begins on the latter of a) 14 days after completing the primary vaccination series (V3 + 14 days) or b) 28 days after initiating treatment for a parasitemia event that was detected on or before V3 + 14 days, whichever comes later. Time-to-event is defined as the number of days between entry into the risk set and date of first *Pf malaria with symptoms*; subjects who do not experience the event by 26 weeks after V3 will be censored from the primary analysis or earlier date of last negative TBS result.

The survival patterns will be described by Kaplan-Meier curves for each arm and compared by the logrank test between two arms. The protective efficacy will be assessed from the Cox proportional hazards model with treatment arm as the regressor, and the vaccine efficacy will be estimated as one minus the hazard ratio.

As a secondary efficacy analysis, the cumulative probability of *Pf malaria with symptoms* through 26 weeks post V3 will be presented for each treatment arm and compared across arms based on Kaplan-Meier estimates along with 95% confidence intervals. This estimation accounts for right censoring and the comparison should be equivalent to Fisher's exact test in case of no censoring.

Sensitivity analyses will include an ITT and ATP analysis with entry into the risk set as with the mITT analysis, and ATP analyses with entries into the risk set at time of first vaccination and at V3.

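### The ITT set used for safety requires person-time in a risk set that opens no earlier than 14 days after V3, so injected children who leave before then drop out of the primary safety proportion

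*Protocol*

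**What the plan says.** **Population.** Protocol 10.3 and SAP 1 define ITT identically: eligible, randomized, one or more injections "with PfSPZ Vaccine or placebo, and contributes evaluable person-time to the risk set".

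**Risk set.** Protocol 10.4.3 (subsection numbered 9.4.3.1) and SAP 3.2.1 state: "Entry into the risk set begins on the latter of a) 14 days after completing the primary vaccination series". The alternative is a later date, 28 days after the start of treatment for an earlier parasitemia. For the ITT analysis the rule is the same: "Sensitivity analyses will include an ITT and ATP analysis with entry into the risk set as with the mITT analysis". Earlier entry is named only for one further group: "ATP analyses with entries into the risk set at time of first vaccination and at V3".

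**Use for safety.** Protocol 10.4.2 and SAP 3.1 state: "The primary safety analysis will be performed using the ITT population and according to treatment received at V1". The endpoint is the "proportion of vaccinees experiencing related SAEs from V1 to 26 weeks after V3" (Protocol 10.1). The other safety endpoints use the same set: "Secondary safety endpoints include the occurrence of unsolicited AEs, laboratory abnormalities, and solicited AEs in the ITT population". Neither document defines a separate safety population.

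**The concern.** Membership of the safety set depends on something that happens after injection. To count, a child must still be under observation at least 42 days after V1 (study day 43 against study day 1). Protocol 8.2 allows an investigator to withdraw a child for an adverse event, and it lists death among the reasons for leaving. The children most informative about early harm are therefore the ones whom the definition can remove.

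For the secondary safety endpoints the condition is sharper still. Their windows close 7 days after each injection or 14 days after V3, which is no later than the day on which the risk set first opens. A child has to outlast the whole window before any event inside it is counted.

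At stake are the primary safety proportion, its exact confidence interval, the Fisher comparison of SAE rates, and the secondary safety tables.

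**Working it through.** **Step 1. The definitions side by side**

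| Analysis | Set | Opens |
|---|---|---|
| Related SAEs (primary safety) | ITT | V1, day 1 |
| Unsolicited AEs, laboratory abnormalities, solicited AEs | ITT | V1, day 1 |
| Efficacy risk set, mITT and ITT | – | V3 + 14, day 43, or later |
| Efficacy risk set, ATP sensitivity analyses only | – | also V1, or V3 |

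A child injected at V1 who leaves before day 43 contributes no person-time to the risk set that applies to ITT. Such a child fails the ITT definition and is absent from the first two rows.

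**Step 2. The plan's own precision figures** (Protocol 10.2, 120 per arm)

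- Event rate giving a 90% chance of at least one event: 1 − 0.1^(1/120) = 1.90%. The plan states 1.9%.
- Upper 95% limit with no events: 1 − 0.025^(1/120) = 0.0303. Table 14 gives 0.030.
- Chance of no event at a 1% rate: 0.99^120 = 0.299, as in Table 13.

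These figures reproduce. They assume that every injected child is observed for the event, and the text applies the 0.030 bound to everyone vaccinated.

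**Step 3. Effect of k children who have a related SAE and leave before V3 + 14 days**

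The documents do not give k, so k = 1 to 3 is an assumption. Limits are Clopper–Pearson 95%, assuming no other events or losses in the arm.

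| Arm | k | ITT as written | All injected |
|---|---|---|---|
| 134 | 1 | 0/133, upper 2.74% | 1/134 = 0.75% (0.02 to 4.09%) |
| 134 | 2 | 0/132, upper 2.76% | 2/134 = 1.49% (0.18 to 5.29%) |
| 134 | 3 | 0/131, upper 2.78% | 3/134 = 2.24% (0.46 to 6.40%) |
| 120 | 1 | 0/119, upper 3.05% | 1/120 = 0.83% (0.02 to 4.56%) |
| 120 | 3 | 0/117, upper 3.10% | 3/120 = 2.50% (0.52 to 7.13%) |

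The Fisher result is unaffected by small k: 1/134 against 0/134 gives p = 1.0 and 5/134 against 0/134 gives p = 0.06. Significance is reached only at 6/134 against 0/134 (p = 0.03). What changes is the reported proportion and its interval.

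**Step 4. Effect on the chance of counting an event**

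Let f be the share of children with a related SAE who leave before V3 + 14 days (assumed). At a true rate of 1.9% and n = 120, the chance of counting at least one is 1 − (1 − 0.019(1 − f))^120. The rate needed for a 90% chance is 1.90%/(1 − f).

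| f | Chance of counting ≥1 | Rate needed for 90% |
|---|---|---|
| 0 | 90% | 1.9% |
| 0.25 | 82% | 2.5% |
| 0.5 | 68% | 3.8% |
| 0.75 | 44% | 7.6% |

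**Step 5. How many children might leave early for any reason**

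Protocol 10.2 assumes 10% drop-out without timing. All of it before day 43 would be 0.10 × 134 = 13.4 children per arm. Spread evenly over the 28 + 182 = 210 days from V1 to 26 weeks after V3, it would be 13.4 × 42/210 = 2.7. Both are scenarios for all leavers, not for children with SAEs.

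**The case against.** **The person-time clause was meant for efficacy.** Several passages support this. The Synopsis and Protocol 4 end the unsolicited-AE window at 14 days after V3 or the last immunization, which matters only if children without V3 count. Safety is analysed by treatment received at V1. Unsolicited AEs are summarized by the preceding vaccination number. Protocol 10.3 sets one or more injections for ITT against all three for mITT. I accept this as evidence of intent. It does not cure the definition; it shows that the documents contradict themselves. A programmer following the SAP would exclude these children, and reinstating them after unblinding would be a post hoc choice.

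**The event would not be hidden.** This stands. A reader might infer that an early related SAE disappears from the safety record. It would not: AEs leading to discontinuation from the study are listed separately, one related SAE in a vaccinee meets a pausing criterion, and related SAEs go to the DSMB. Protocol 10.1 also describes the primary safety endpoint as descriptive. None of these routes restores the child to the primary proportion or its interval.

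**Stronger readings that the documents do not support:**

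- *V3 + 14 days is the only risk-set entry defined.* Entry at V1 and at V3 is also named, but only for ATP sensitivity analyses.
- *ITT and mITT contain the same children.* On the literal text a child who stops injections never completes the series, so never enters. But Protocol 8.2 keeps such children in the study, and no entry date is given for them. The rule may equally be read as undefined.
- *About 13 vaccinees per arm would be lost from the safety set.* That requires all drop-out to fall before day 43, and no timing is stated.
- *The ATP analysis from V1 is seriously biased because ATP is selected on later completing V3 in window.* The selection exists, but Protocol 5.2.3 expects dosing in the dry season with almost no transmission, so malaria before V3 should remove few children. The 28 of 210 days (13%) involved is a share of calendar time, not a measure of bias.

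**Conclusion.** The point holds as a defect of definition present in both documents. As written, any child injected at V1 who leaves before V3 + 14 days is outside the numerator and denominator of the primary safety proportion, its exact interval and the Fisher test, and outside the secondary safety tables. A child with a related SAE who receives all three injections and stays until the risk set opens is counted normally.

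The size cannot be fixed from the documents, because neither the number nor the timing of early exits is given. One affected child is enough to change the headline from no related SAE (upper limit 2.7%) to one (0.75%, upper limit 4.1%). With related SAEs expected to be rare, that is a material change to the primary safety statement, although it would not change a test result.

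The efficacy part is weaker. The ITT sensitivity analysis may add no one to mITT, in which case it would not test the effect of excluding incomplete vaccinees. That rests on the literal reading; on the other reading the entry date is simply missing.

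**What to change.** 1. Define a Safety Population in Protocol 10.3 and SAP 1: all children who receive at least one injection, analysed by product received at V1, with no person-time condition. Use it for every primary and secondary safety endpoint in Protocol 10.4.2 and SAP 3.1.
2. In those two sections, end the unsolicited-AE window as the Synopsis does, so that it is defined for a child without V3.
3. Keep the person-time condition for efficacy only, and say so.
4. State a risk-set entry date for ITT children without V3, for example scheduled V3 + 14 days (study day 43), so that the ITT sensitivity analysis includes incomplete vaccinees who are still followed.
5. Optional and minor: run the from-V1 analysis in ITT as well as in ATP.

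The cost is wording in two documents, to be settled before unblinding, with no new data collection. Item 4 reaches only children who remain under observation. Protocol 8.2 also lets the investigator withdraw a child from the study, so follow-up to day 43 is not guaranteed.
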